9.2 Sample Size and Randomization

Sample Size and Power Estimation: Although this study will test for statistical significance, the primary aim of this pilot RCT is to estimate the intervention's effect size to conduct a more definitive R01 study, as is outlined in NIH guidelines for developing behavioral interventions³³. The study was powered conservatively based on an 80% (n=64) ITT sample. Effect sizes for the degree of change in IDS-CR (primary outcome) were estimated for the hyperthermic yoga versus the control using Cohen's d (effect size for t-test). A power analysis found that with an ITT sample of 64 (32 per arm), a two-tailed t-test with an alpha level of .05 will yield a statistical power of 79% to detect a large effect size of .70 and 50% to detect a moderate effect size (.50). Thus, if the effect size falls between moderate and large, power would approach 80%, since the evaluable sample should be between 64 and 80. Preliminary data suggested a moderate effect size of .54 for depression³⁴. We predict a more robust effect size of at least .60-.70, as this is a larger sample recruited specifically for depressive symptoms.

Randomization: Our biostatistician will establish the blind and deliver it to the designated Research Coordinator. Randomization will be done by random permuted block design in blocks of 2 and 4. This method assigns subjects to each intervention group with equal probability, while at the same time generating a balanced design. The random permuted block randomization method also protects against bias due to temporal trends (e.g., experience of research staff, or seasonal effect). This randomization design should balance the heterogeneity of the subjects between groups.

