Primary Aim II: To collect the Inventory of Depressive Symptomatology – Clinician Rated (IDS-CR) scores at screening; baseline; and weeks-1, -3, -5 and -8 to evaluate the efficacy of hyperthermic yoga for depressive symptoms.

Hypothesis II: The IYG will have greater decreases in Inventory of Depressive Symptomatology – Clinician Rated (IDS-CR) scores after 8-weeks compared to the DYG.

Response over 8-weeks defined by 50% or greater decrease on IDS-CR total; remission ≤ 11 on IDS-CR total. Continuous variables will be analyzed by generalized mixed effect modeling, which impute missing values based on maximum likelihood estimates of missing parameters, allowing analysis of all MITT participants. A time-by-condition interaction will be analyzed to test the intervention's efficacy. Relevant potential covariates (e.g., attendance) will also be examined.

Primary Aim III: To collect (a) physiological and (b) psychological mediators of hyperthermic yoga in the IYG and DYG group at screening; baseline; weeks-1, -3, -5 and -8 to evaluate treatment response in the IYG compared to the DYG.

Hypothesis IIIa: Salivary cortisol, and inflammatory markers (i.e., Tumor Necrosis Factor [TNF- α], Interleukin-6 [IL-6], and C-Reactive Protein [CRP]) will significantly decrease, following 5- and 8-weeks of hyperthermic yoga in the IYG compared to the DYG.

Hypothesis IIIb: Perceived stress, mindfulness, and rumination will improve by 5- and 8-weeks in the IYG compared to the DYG.

Latent growth curve modeling will assess potential mechanisms of the treatment effect. The slope (change over time) of the mediator variables will be regressed upon the independent variable (condition). The slope of the dependent variable will also be regressed upon the slope of the mediators. This model will permit assessment of the change in mechanisms as it predicts the change in the dependent variables.

Secondary Aim I: To collect measures of quality of life, general health, physical functioning, decreased perceived stress, anxiety, and sleep in the IYG and DYG at screening; baseline; and weeks-1, -3, -5 and -8 to evaluate hyperthermic yoga for secondary outcome measures.

Secondary Hypothesis I: The IYG will have significant improvements in quality of life, general health, physical functioning, perceived stress, anxiety, and sleep compared to the DYG.

These will be analyzed by the same methods as outlined for Primary Aim II (above).

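### The 79% power was calculated for a t-test on IDS-CR change, but efficacy is tested by a time-by-condition interaction whose form is not stated; the week-8 contrast should be named as the decisive test

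*Combined protocol and SAP*

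**What the plan says.** - **Hypothesis (sections 1.1 and 9.6).** Hypothesis II is a greater IDS-CR decrease in the immediate yoga group (IYG) than in the delayed yoga group (DYG) after 8 weeks. Section 6.2.5 labels Visit 6, week 8, as the primary endpoint for both groups.
- **Power (section 9.2).** "Effect sizes for the degree of change in IDS-CR (primary outcome) were estimated" using Cohen's d. For 64 analysed participants, half of them in each group, the section states that "a two-tailed t-test with an alpha level of .05 will yield a statistical power of 79% to detect a large effect size of .70". A second figure is 50% at d = .50. The 64 is 80% of the 80 to be randomised. Section 9.2 also says that the pilot's primary aim is to estimate the effect size for a later study.
- **Test (section 9.6, Primary Aim II).** IDS-CR is collected as "scores at screening; baseline; and weeks-1, -3, -5 and -8", six occasions in all. Continuous outcomes go into a mixed-effects model, and "A time-by-condition interaction will be analyzed to test" efficacy. The section does not say whether time is categorical or linear, whether screening enters the model, what the covariance or random effects are, or which contrast decides.

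Neither section 9.2 nor section 9.6 gives a power calculation for an interaction or a repeated-measures model.

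**The concern.** The hypothesis, the power calculation and the test should refer to the same quantity. Here the first two point to one number, the group difference in change at week 8, and the third does not.

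With categorical time, the interaction asks whether the group difference varies at all across visits. A difference at week 3 that has gone by week 8 would count as a positive result. With linear time, the interaction asks whether the slopes differ. A benefit that is complete by week 1 and then holds is poorly described by a slope and may be missed. The choice between them is left until after the data are in.

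Three things are at stake. The main efficacy conclusion may depend on a coding decision that was not made in advance. The stated power may not describe the test that is run. A multi-df F test also gives no single effect size, which is what section 9.2 says the pilot is for. Secondary Aim I inherits the same analysis and so the same gap.

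**Working it through.** **Step 1: the plan's own figure.** Inputs from section 9.2: n = 32 per arm, two-sided alpha .05, d = .70 and .50. The noncentrality is d × √(n/2) = d × √16 = 4d, with 62 df.
- d = .70: noncentrality 2.8, power 78.7%.
- d = .50: noncentrality 2.0, power 50.4%.

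Both stated figures reproduce for a two-sided t-test on change.

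**Step 2: the interaction at the same week-8 effect.** The documents give no covariance and no trajectory, so these are my assumptions. In every case the baseline-to-week-8 change differs by .70 change-score SDs, with complete data and 32 per arm. Visits are baseline and weeks 1, 3, 5 and 8. Let f be the fraction of the week-8 effect present at each visit.
- *Omnibus test, 4 and 59 df:* λ = (n/2) m′W⁻¹m, where m holds the group differences in change from baseline at the four later visits and W is the covariance of those changes.
- *Linear slope:* generalised least squares slope, noncentral t with 62 df.

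Under compound symmetry these have a closed form. The change-score SD is σ√(2(1−ρ)), so ρ cancels:
- λ = 16 × (.70² × 2) × Σ(f − f̄)² = 15.68 × Σ(f − f̄)².
- Slope noncentrality = √15.68 × Σ(t − t̄)f / √Σ(t − t̄)². Here t̄ = 3.4 and Σ(t − t̄)² = 99 − 5 × 11.56 = 41.2.

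Two worked cases:
- *Linear divergence,* f = (0, .125, .375, .625, 1). Σ(f − f̄)² = 1.5469 − 5 × .425² = .6438, so λ = 10.09 and omnibus power is 68%. The slope noncentrality is 3.960 × 5.15/6.419 = 3.18, power 88%.
- *Full effect from week 1,* f = (0, 1, 1, 1, 1). Σ(f − f̄)² = 4 − 16/5 = .8, so λ = 12.54 and omnibus power is 79%. The slope noncentrality is 3.960 × 3.4/6.419 = 2.10, power 54%.

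The full grid adds exponentially decaying correlation, with a baseline-to-week-8 correlation of .3 to .7:

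| Trajectory | 4-df, comp. symm. | 4-df, decay | Slope, comp. symm. | Slope, decay |
|---|---|---|---|---|
| Linear | 68% | 56% | 88% | 79% |
| Full by week 3 (one third at week 1) | 83% | 88–94% | 86% | 78–79% |
| Full from week 1 | 79% | >99% | 54% | 75–78% |
| Half at week 5 | 79% | 73–78% | 91% | 79–80% |
| Week 8 only | 79% | 88–94% | 80% | 78–79% |

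The week-8 change contrast has 78.7% in every row. A random-intercept-and-slope covariance, at two slope variances, gives 63–91% for the 4-df test and 50–89% for the slope.

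**Step 3: significance without a week-8 benefit.** Take a difference of the same size at week 3 only, f = (0, 0, 1, 0, 0). Then Σ(f − f̄)² = 1 − 1/5 = .8 and λ = 12.54 again. Under compound symmetry the omnibus test rejects 79% of the time although the true week-8 difference is zero. The week-8 contrast would reject 5% of the time.

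**Step 4: screening as a sixth time level.** I assume it falls at week −2. The 5-df test then ranges from 52% to above 99% for correlations of .4 to .6. With the full effect from week 1 and compound symmetry, omnibus power moves from 79% to 94% and slope power from 54% to 92%. Whether screening enters is therefore not a detail.

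**The case against.** The best defence is that a t-test on change is a common planning approximation for a mixed model, that an interaction also tests differential change, and that the arithmetic in section 9.2 is right. If the interaction is read as the baseline-to-week-8 contrast with complete data, 79% applies. Section 9.2 says only change and names no visit; I infer the week-8 link from Hypothesis II and section 6.2.5. All this stands, but the plan neither says that the t-test is an approximation nor names that contrast.

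It can also be said that this is a pilot aimed at estimation. That limits the consequence, but it favours a named contrast, which gives an estimate with an interval.

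Two stronger readings are tempting and are not supported:
- *That 79% overstates the power.* The table has entries on both sides of 79% for both tests. The 4-df test falls clearly below it under linear divergence, but is at or above it in most of the other cases.
- *That the model includes screening scores and is weakened by them.* Section 9.6 lists screening as a collection point and does not say that it is a time level. A pre-randomisation score can add precision, as step 4 shows, and the entry threshold of >23 applies to both arms.

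**Conclusion.** The point holds as a mismatch between the powered test and the planned test, not as an error in the power calculation or as evidence of low power. The 79% belongs to an unadjusted two-sample comparison of change. For the interaction at the same week-8 effect, power is about 56% to above 99% (4-df omnibus) and 54% to 91% (linear slope without screening), with a low end near 50% for the slope if subjects also have random slopes. These ranges rest on assumed covariances, five assumed trajectories and complete data; other shapes could fall outside them. That an omnibus result need not mean a week-8 benefit, and that a slope can miss an early sustained one, does not depend on the exact ranges. The consequence is moderate, since the outcome and the time point are already fixed and only the form of the test is open. It should be settled before the data are analysed.

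**What to change.** In section 9.6, Primary Aim II:
- Name the IYG-minus-DYG difference in IDS-CR change from baseline (Visit 2) to week 8 as the single decisive contrast. Estimate it with a 95% CI from the mixed model with categorical time, and state the covariance structure.
- State that screening is not a time level, or exactly how it enters.
- Report the overall time-by-condition interaction as supportive.

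In section 9.2, tie the 79% to this contrast as a complete-data planning figure.

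Baseline adjustment is optional. At the same change-score effect, the standardised effect becomes .70 × √(2/(1 + ρ)), which is .84 at ρ = .4 and .78 at ρ = .6. Power is then about 91% and 87%, so the 79% would be conservative for that version.

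The cost is SAP wording, with the same data and the same model family. There is also some loss of power against a slope test if the true divergence is linear: 79% against 88% under compound symmetry, and none under decaying correlation.

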10. DATA COLLECTION AND QUALITY ASSURANCE

10.1 Data Collection Forms

Data will be collected on the specified CRFs. The Research Coordinator will be responsible for collecting all self-report and other non-doctoral level staff CRFs. We will designate a blinded Coordinator (not the primary Research Coordinator for the study) to manage the assessment data vis-a-vis quality checking, entering it in the database, and assisting with analysis, as needed. Doctoral level staff conducting clinician-ratings and/or medical assessments will be responsible for completing the appropriate CRFs. Blinded assessors will complete an IDS-CR, the primary study endpoint. All forms will have a participant ID with no other identifying information, as specified in section 11.3 below.

10.2 Data Management

Self-report data provided by study subjects will be reviewed by blinded study staff for completeness and quality (such as multiple answers when one response is allowed) and all attempts will be made to solve problems prior to the subject leaving the premises. Any incomplete data, illegible, or questionable data provided by blinded assessors will be resolved through feedback with the clinician, within one day following the study visit. This study will utilize REDCap (Research Electronic Data Capture), a browser-based, metadata-driven EDC software solution and workflow methodology for designing clinical and translational research databases. REDCap is secured with password protection. Individual subjects' information will be entered into the database using study ID numbers. No personal identifiers will be stored.

The REDcap system will flag any remaining data quality problems (such as data values outside the expected range) during data entry; any problems will be resolved before the record is added to the database. Extensive quality control procedures for handling and assaying laboratory samples will be carried out to ensure complete and valid biological data. Early in the study and periodically throughout the period of data collection, data will be reviewed by the study Statistician for completeness, consistency, and other indicators of data quality in a

blinded fashion. Missing data will be described but will be inexplicitly imputed in all analyses by using only available data. All primary endpoint data will be quality-assured and assessed by blinded raters. Any errors in completion will be reviewed to determine if directions or procedures need to be altered. In this case, permission from the IRB will be requested to change any procedure. If it is determined that patients are misinterpreting any instrument and answering incorrectly as a result, they will be given proper clarification and instruction.

10.3 Quality Assurance

10.3.1 Training

All staff engaged in human subjects research are required to complete the Collaborative Institutional Training Initiative (CITI) human subjects training and refresher training every three years to be involved with human subject research.

Yoga instructors and studio owners at Bikram Yoga Boston and Bikram Yoga Cambridge will undergo Partners IRB approved modified CITI training by the PI.

10.3.2 Quality Control Committee

N/A

10.3.3 Metrics

Missing data will be handled as specified in section 9.6. Data entry will be double checked by another individual.

10.3.4 Protocol Deviations

Protocol deviations will be collected and documented on the Protocol Deviation Log by the Research Coordinator, overseen by the PI. The PI and at least one member of her mentoring team will review these deviations for potential amendment to IRB approved protocol.

10.3.5 Monitoring

The DSMB, NCCIH, the Partners IRB, and/or OHRP will be monitoring the protocol compliance, data quality, and consent forms.

10.3.6 Data Use Agreement

In addition to the previously described samples analyses, we intend to obtain a Data User Agreement in order to collaborate and share data with an undergraduate student being mentored by [name], whose previously approved study utilizing both assessment measures and biological data from the current protocol. The student is completing an undergraduate thesis and is affiliated with UCSI University in Malaysia, and holds an RA position at Harvard Medical School. The fully processed and deidentified data from this protocol with [name] will be used for a requisite to complete his dissertation and ultimately graduation. All data will be securely stored in MGH Dropbox and Harvard Medical School (HMS) O2 High Performance computing (HPC) cluster. The data will not be transferred from the HMS O2 HPC cluster. Upon approval of the DUA, the fully processed data in the form of graphs and summary tables will be transferred to UCSI servers using a secure file transfer portal using HMS resources. All data associated with the DUA will be de-identified. The student will be monitored and mentored remotely by [name]. No data will leave the HMS cluster or Boston. The data being utilized is

from blood samples that are currently being processed for gene expression (RNA sequencing) and from clinician-rated primary outcome measures. No samples will be physically removed from the MGH premises.

11. PARTICIPANTS RIGHTS AND RESPONSIBILITIES

11.1 Institutional Review Board (IRB) Review

This protocol and the informed consent document and any subsequent modifications will be reviewed and approved by the Partners IRB.

11.2 Informed Consent Forms

A signed consent form will be obtained from each participant. The consent form will describe the purpose of the study, the procedures to be followed, and the risks and benefits of participation. A copy will be given to each participant and this will be documented in the participant's record.

11.3 Participant Confidentiality

Any data, specimens, forms, reports, and other records that leave the site will be identified only by a participant identification number (Participant ID, PID) to maintain confidentiality. All identifiable records will be kept in a locked file cabinet. All computer entry and networking programs will be done using PIDs only. Information will not be released without written permission of the participant, except as necessary for monitoring by IRB, the NCCIH, and the OHRP.

11.4 Study Discontinuation

The study may be discontinued at any time by the Partners IRB, the NCCIH, the OHRP, or other government agencies as part of their duties to ensure that research participants are protected.

12. COMMITTEES

Advisory Committee: All mentors (Drs. [name], [name], and [name]) will meet quarterly as an Advisory Committee throughout the PI's K23 Award. The committee will provide guidance such that the following goals are met: 1) recruitment does not fall below 75% of projection, 2) treatment adherence is sufficient, and 3) authorship and future grant submission goals are met. [name] will oversee the PI's formal progress evaluations.

13. PUBLICATION OF RESEARCH FINDINGS

The study governance includes an Advisory Committee (see 12 above). Publication of the results of this trial will be governed by the policies and procedures developed by the Advisory Committee. Any presentation, abstract, or manuscript will be made available for review by the sponsor and the NCCIH prior to submission.

